5.2 Post-Treatment Assessment (Visit 2)

Visit 2 will occur 7 to 14 days after randomization. During this visit, the following procedures will be performed:

- Obtain vital signs after sitting for 5 – 10 minutes ([Section 4.5](#)).
- Perform urine pregnancy test.
- Perform pelvic examination including vaginal wall inspection (a naked eye inspection), examination of the cervix, and Investigator’s assessment of local site reactions.
- Record subject-assessed local site reactions (e.g., itching, burning/stinging, localized pain).
- Perform clinical test of response by assessing the subject for presence of these three of the Amsel’s criteria:
 - Resolution of the abnormal vaginal discharge characteristic of BV to a normal physiological discharge; AND
 - Negative “whiff test” after addition of a drop of 10% KOH to vaginal discharge; AND
 - Presence of clue cells at <20% of the total epithelial cells on microscopic examination of the saline wet mount.
- Determine if vaginal pH is <4.7, which is part of the assessment of therapeutic cure (defined as clinical cure, vaginal pH <4.7 and bacteriological cure).
- Record concomitant medications taken since the prior visit along with the indications for the medications.
- Study medication remaining in the tube will be returned by subjects, including unused applicators. Verify that the subject inserted the medication according to instructions and for five consecutive days.
- Assess and record AEs.

- Confirm the date of the subject's Visit 3 will still likely occur on a day that the subject is not expecting menstruation. Note: The subject should not be menstruating during the five days of study medication administration or be scheduled for Study Visits 2 or 3 when menstruating in order for assessments to be accurate.

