6.2 Subject Discontinuation

A subject may be withdrawn from the study prior to completion for any of the following reasons:

- AEs
- Abnormal laboratory values
- Death
- Lack of efficacy
- Lost to follow-up
- Noncompliance with study drug
- Physician decision
- Pregnancy (if applicable)
- Protocol deviation
- Study terminated by Sponsor
- Withdrawal by subject; NOTE: if the subject decides to withdraw from the study due to an AE then it should be classified as withdrawal due to an AE.
- Other (e.g., any reason that may affect the outcome of the study or safety of subjects)

If a subject withdraws prematurely for any reason, the site should make every effort to have the subject return for her next scheduled visit to perform all required visit activities and to collect and reconcile all test article. If the subject is discontinued prior to the Assessment of Clinical Cure Visit (Visit 3; Day 21 to 30), the site should complete the End of Study eCRFs during the last visit that the subject will complete. Subjects who withdraw prematurely will not be replaced. When a subject is withdrawn from the study for a treatment-related AE (i.e., as defined in [Section 8.1.2](#)), when possible, the subject should be followed until resolution or stabilization of the AE. If a subject is discontinued from the study due to pregnancy, the pregnancy and its outcome should be followed (see [Section 8.1.5](#)).

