3.4 Analysis Populations

All Screened Population: all subjects who signed Consent Form and screened at the study sites.

Intent-to-Treat (ITT) Population: All randomized subjects.

Safety Population: All randomized subjects who received at least 1 dose of study drug. If the drug accountability is unknown (e.g., due to being lost to follow-up after being randomized) then subjects will be assumed to have taken study drug and included in the safety population. Subjects reporting 0 doses will be excluded.

Modified Intent-to-Treat (mITT) Population: a subset of the Safety Population who also met all 4 Amsel's criteria at baseline, but excluding those who subsequently demonstrate a positive or indeterminate test result for other concomitant vaginal or cervical infections at baseline (e.g. *C. trachomatis*, *N. gonorrhoeae*) which may interfere with the efficacy assessment for BV, or who have a baseline Nugent's score < 4. If baseline STI value is missing, use the Post-Treatment Assessment Visit infection test result. Subjects without a Nugent's score at baseline will be excluded from the mITT population.

Per Protocol (PP) Population: All mITT subjects except for those who had at least one of the protocol deviations listed below. If lack of efficacy (LOE) is the discontinuation reason and the subject took at least 3 doses, then the subject will be included in PP as a treatment failure and then the 6 protocol deviations below will not exclude those subjects:

1. Used topical or systemic antimicrobial drugs after randomization, this includes the following drug classes: antimycotics, antibacterials, antiprotozoals, gynecological anti-infectives, antiseptics and antifungals.
2. Used non-study vaginal products during the study
3. Did not start treatment within 2 days of randomization
4. Took less than 5 doses of study drug
5. Test of cure visit (V3) was not in the Study Day 22 – 31 window, i.e., Visit 3 was not 21 – 30 days after randomization
6. Test of cure visit (V3) not done

Other important violations that represent material non-compliance with study drug or protocol that would impact the primary and secondary efficacy endpoints will be reviewed prior to database lock (i.e., before unblinding). These will be documented in the Evaluability Memo which will be included in the clinical study report.

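### SAP 3.4 keeps a non-responder with a listed deviation in Per Protocol only through a lack-of-efficacy discontinuation code, so some women treated for persistent BV leave the equivalence test

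*SAP*

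**What the plan says.** SAP 3.4 defines PP as "All mITT subjects except for those who had at least one of the protocol deviations listed below". Two of the six deviations matter here:

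- Deviation 1: "Used topical or systemic antimicrobial drugs after randomization, this includes the following drug classes: antimycotics, antibacterials, antiprotozoals, gynecological anti-infectives, antiseptics and antifungals".
- Deviation 6: "Test of cure visit (V3) not done".

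There is one exception: "If lack of efficacy (LOE) is the discontinuation reason and the subject took at least 3 doses, then the subject will be included in PP", counted as a treatment failure. For such women "the 6 protocol deviations below will not exclude those subjects". The closing paragraph of SAP 3.4 then says that early leavers without an outcome assessment are failures in mITT but are not in PP. It makes no allowance for the lack-of-efficacy exception.

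On the coding, Protocol 6.2 opens its list with "A subject may be withdrawn from the study prior to completion for any of the following reasons". Lack of efficacy is one of twelve entries, beside physician decision, protocol deviation, withdrawal by subject and other. Protocol 3.4 asks for the primary reason from that list. Protocol 3.5.10 bars antibiotics during the study, but nothing ties their use to a lack-of-efficacy code or defines it as failure.

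On the data, Protocol 5.2 requires sites to "Record concomitant medications taken since the prior visit along with the indications for the medications". Protocol 5.3 and 5.4 repeat this for Visit 3 and early termination.

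SAP 3.7 and 3.7.1 test equivalence in PP. The only equivalence table listed (14.2.1) is for PP.

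**The concern.** Take two women who each used at least 3 doses, still had BV at Visit 2 and were then given a non-study antibacterial for it. One is discontinued with lack of efficacy recorded, and she is a PP failure. The other stays to Visit 3, or leaves with a different reason recorded, and deviation 1 deletes her. Their treatment outcome is the same; only the disposition record differs.

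The exception shows that the plan already accepts the principle: a non-responder with adequate exposure should count as a failure even if she took a prohibited drug. The trigger chosen does not deliver that principle consistently. The resulting exclusion depends on outcome, because it removes failures and never cures. It also acts on the only population in which equivalence is tested, and no planned mITT equivalence analysis would show its effect.

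**Working it through.** **1. The rule applied case by case** (mITT women, not cured, at least 3 doses)

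| Course | Listed deviation | PP status |
|---|---|---|
| 5 doses, no other drug, Visit 3 in window, no other deviation | none | failure, on observed result |
| Leaves before Visit 3, coded lack of efficacy, treated or not | 6, and 1 if treated | failure, by the exception |
| Treated for BV, stays to Visit 3 | 1 | deleted; there is no discontinuation reason to code |
| Treated for BV, leaves before Visit 3 under another reason | 1 and 6 | deleted |

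The Evaluability Memo covers further violations found at blinded review. It states no route for restoring a deleted subject.

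**2. The plan's own figure.** Protocol 9.1: 36% vs 20%, 90% power, with the two-sided 0.05 level of 9.6.1. The continuity-corrected two-proportion formula gives 176 per arm. Then 176 / 0.876 = 200.9, taken as 201, and 3 × 201 = 603, as stated. Equivalence power with 176 per arm at 36% vs 40% is about 91%. The sample size is not in dispute.

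**3. Inputs for the deletion check.** 738 randomized, 246 per arm; 246 × 0.876 = 215.5, taken as 215 mITT women per arm. Interval from SAP 3.7.1: difference ± [1.645 se + (1/n_T + 1/n_R)/2], with both limits within ±0.20. Assumptions not in the documents: the share r of each arm's failures that is deleted, and no other PP loss.

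For true cure rate p, let k = 1 − (1 − p)r. Retained n = 215k and PP cure rate = p/k.

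Example, 30% vs 50% with r = 20% (test) and 10% (reference):

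- Test: k = 1 − 0.70 × 0.20 = 0.86; n = 184.9; PP cure = 0.30/0.86 = 34.9%.
- Reference: k = 1 − 0.50 × 0.10 = 0.95; n = 204.25; PP cure = 0.50/0.95 = 52.6%.
- Observed difference: −17.7 points instead of −20.

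The probability of declaring equivalence is the exact binomial sum over all outcome pairs that meet the SAP rule, with n rounded.

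| True cure, test vs reference | Failures deleted, test/reference | PP difference (points) | P(declare equivalence) |
|---|---|---|---|
| 30% vs 50% | 0/0 | −20.0 | 4.0% |
| | 10%/5% | −19.0 | 5.7% |
| | 20%/10% | −17.7 | 9.6% |
| | 30%/10% | −14.7 | 23.8% |
| | 20%/20% | −20.7 | 3.0% |
| | 10%/20% | −23.3 | 0.7% |
| 16% vs 36% | 0/0 | −20.0 | 3.9% |
| | 10%/5% | −19.7 | 4.4% |
| | 20%/10% | −19.2 | 5.3% |
| | 30%/20% | −19.9 | 3.9% |
| | 30%/10% | −17.1 | 12.3% |
| | 20%/20% | −22.1 | 1.3% |
| 36% vs 40% (power) | 0/0 | −4.0 | 95.4% |
| | 20%/20% | −4.2 | 90.8% |

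**4. Why equal shares do not help a worse test gel at these rates.** With a common r, the PP difference is the true difference times (1 − r)/(k_T k_R). At 30% vs 50% and r = 0.20 the factor is 0.80/(0.86 × 0.90) = 1.03. At 16% vs 36% it is 0.80/(0.832 × 0.872) = 1.10. The gap widens slightly. The factor falls below 1 only when p_T + p_R + r(1 − p_T)(1 − p_R) exceeds 1. Here that sum is 0.80 + 0.07 = 0.87 and 0.52 + 0.11 = 0.63.

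**The case against.** **Removing users of prohibited antimicrobials is ordinary PP practice.** This is fair as a general position, but the SAP has already departed from it by waiving deviation 1 for lack-of-efficacy leavers. The question is only whether that waiver is applied consistently.

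**A site withdrawing a woman with persistent BV would naturally record lack of efficacy as the primary reason.** This is plausible, and the documents do not show how often another code would be used. It does not help the woman who stays to Visit 3, since she has no discontinuation reason at all.

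**Nothing suggests that deletion would differ between two blinded 0.75% gels with the same listed ingredients.** This stands. Inflation needs a higher chance of deletion given failure in the test arm, and the documents give no evidence of that. At cure rates near the planned 36%, moderate imbalances also do little (5.3% at 20%/10%, 3.9% at 30%/20%).

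A reader might infer three stronger points that the documents do not support:

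- *That every non-responder needs a lack-of-efficacy code to count in PP.* She does not if she has none of the six deviations; her observed Visit 3 result counts.
- *That a test gel which merely fails more often gains from the rule.* At 30% vs 50% with 20% of failures deleted in each arm, about 30 test and 21.5 reference failures go, yet the gap widens to −20.7 points and false equivalence falls to 3.0%.
- *That the rule always biases toward equivalence.* With the shares reversed (10%/20%) it is conservative, at 0.7%.

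**Conclusion.** The point holds within limits. Among non-responders with a listed deviation, PP status turns on a lack-of-efficacy code together with at least 3 doses. Women with the same exposure who were treated for persistent or recurrent BV and stayed, or left under another reason, are deleted from the population that decides equivalence.

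The size is uncertain because no rescue rate is given. With 215 per arm and the SAP interval, false equivalence at the margin starts near 4%. It reaches 5.3% to 9.6% when 20% of test and 10% of reference failures are deleted, and 12.3% to 23.8% at 30% and 10%; the lower figure in each pair is for the planned 36% reference rate. At these cure rates a larger deleted share in the test arm is necessary for inflation, but not always sufficient. Deleting 20% in both arms gives 1.3% to 3.0% at the margin and lowers power from 95% to 91% at 36% vs 40%.

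This should be corrected before lock because the remedy is cheap and the classification should not depend on a disposition code. It does not show that the trial's conclusion would be wrong.

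**What to change.** In SAP 3.4:

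1. Keep the existing lack-of-efficacy route. Replacing it would delete lack-of-efficacy leavers who took no other drug, through deviation 6.
2. Add a second route. Any mITT subject who took at least 3 doses and then, before her Visit 3 assessment, received a non-study BV-active drug with a recorded indication of persistent or recurrent BV is a PP treatment failure. This applies whatever the disposition reason and whether or not she stayed in the study, and deviations 1 to 6 do not exclude her.
3. Continue to exclude women given antimicrobials for other indications.
4. Assign cases blind, before database lock, from the recorded indication, and list them in the Evaluability Memo.
5. Amend the closing paragraph of SAP 3.4 so that its exclusion of failures without outcomes does not apply to women kept by either route. At present it conflicts even with the existing exception.

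This changes analysis classification only, not how any woman is managed. The cost is SAP wording, since indications are already collected. A few will need blinded adjudication, and observed PP cure rates will be slightly lower.

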Subjects in the mITT population who discontinue early from the study, and do not have an assessment of Clinical Cure or Bacteriological Cure will be included in the mITT population as treatment failures. These subjects without actual outcomes, but are classified as treatment failures will not be included in the PP analysis population.

sm **W W I** **W**

Subject demographics and pre-treatment characteristics will be summarized for the ITT analysis population, and some of these summaries may also be done for other populations when deemed important.

sharp

A summary of demographics and subject characteristics will be created for the ITT, Safety, mITT, and PP populations, and include age, race, ethnicity, height, weight, and body mass index (BMI) at the study entry visit with:

- 6-number statistics (number of non-missing observations, mean, median, SD, minimum, and maximum) for age, height, baseline weight, baseline BMI (to be calculated, see formula in [Section 3.8.4](#)) by treatment group and for all subjects.
- Age will be calculated (with the INTCK function in SAS®) using the study entry visit date and the date of birth. Subject age (years) will also be categorized as 18-20, 21-30, 31-40, 41-50, 51+, and then summarized categorically along with race, ethnicity.
- BMI at the study entry visit will also be categorized as: Underweight (< 18.5), Normal (18.5 – 24.9), Overweight (25.0 – 29.9), and Obese (≥ 30.0). The number and percentage of subjects in each of these categories will be presented by treatment group and for all subjects.

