3.7 Efficacy Analyses

The mITT population will be used to compare both the test and reference products to placebo. The PP population will be used to evaluate therapeutic equivalence between the test and reference product.

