3.7.1 Primary Efficacy Analyses

Primary efficacy endpoint is the “Clinical Cure” at the Test of Cure (TOC) visit (Visit 3) and includes the following 3 parameters from the “Study Procedure” CRF page:

- Resolution of the abnormal vaginal discharge to a normal physiologic discharge, which is from the variable *SPCDBV* (*Was there clinical diagnosis of bacterial vaginosis?*), with value of “No”
- Negative whiff test, which is from the variable *SPWWT* (*Was there a positive whiff test after adding a drop of 10% KOH to vaginal discharge?*), with value of “No”

- Presence of clue cells at < 20% of the total epithelial cells on microscopic examination of the saline wet mount, which is from the variable *SPSWM*, with value of "No".

To investigate therapeutic equivalence, the 90% confidence interval (CI) for difference, [test - reference], in proportion of subjects achieving "Clinical Cure" will be calculated, using the PP analysis population. Adopted from [FDA Office of Generic Drugs Draft Product Specific Guidance for Generic Drug Development on Metronidazole \(Recommended April 2013\)](#) document, the compound hypothesis to be tested here is:

$$H_0: p_T - p_R \leq -0.20 \text{ or } p_T - p_R \geq 0.20$$

versus

$$H_A: -0.20 \leq p_T - p_R \leq 0.20$$

where p_T = cure rate of test treatment and p_R = cure rate of reference treatment.

Let

n_T = sample size of test treatment group

$c n_T$ = number of cured subjects in test treatment group

n_R = sample size of reference treatment group

$c n_R$ = number of cured subjects in reference treatment group

$$P_T = c n_T / n_T, \quad P_R = c n_R / n_R,$$

$$\text{and } \text{se} = (p_T(1 - p_T)/n_T + p_R(1 - p_R)/n_R)^{1/2}$$

The 90% confidence interval for the difference in proportions between test and reference was calculated as follows, using Yates' correction

$$L = (p_T - p_R) - 1.645 \text{ se} - (1/n_T + 1/n_R)/2$$

$$U = (p_T - p_R) + 1.645 \text{ se} + (1/n_T + 1/n_R)/2$$

If the lower limit $L \geq -0.20$ and upper limit $U \leq 0.20$, we will reject null hypothesis H_0 and claim the bioequivalence ("Therapeutic Equivalence") of test treatment GDC-229 and reference treatment.

Two-sided 90% confidence interval (CI), with continuity correction, for the "Clinical Cure" rate of each treatment arm will also be presented, with the following formula:

$$\hat{p} \pm (z_{\alpha/2} \times se(\hat{p}) + (1/2n))$$

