where p is the percentage (proportion) of subjects with “Clinical Cure”, $z_{\alpha/2}$ is the standard normal distribution’s 5th percentile (with $\alpha = 0.1$), and n is the analysis population size in the relevant treatment group, with standard error for the proportion.

$$se(\hat{p}) = \sqrt{\hat{p}(1-\hat{p})/n}$$

PROC FREQ (SAS 9.4) will be employed for the analysis. Proportion of subjects with “Clinical Cure” in test product GDC-229 and reference drug will also be compared against that in placebo group, and p values from chi-square test, or Fisher’s exact test - if any cells have expected frequency of < 5, will be presented. As a parameter for determining adequate study sensitivity, both test product and the reference drug need to have higher “Clinical Cure” rates than placebo and with p values < 0.05, using the mITT analysis population and Last Observation Carried Forward (LOCF), which means if no assessments are available at End of Trial visit (either Visit 3 for completers, or Early Termination (visit 4) for discontinued subjects), then the Visit 2 assessment results will be used. A 95% CI for the “Clinical Cure” rate of each treatment arm will be presented for mITT subjects. The formula for this 95% CI will be the same as above 90% CI except for replacing the α value with 0.05.

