3.7.2 Secondary Efficacy Analyses

The endpoints for secondary efficacy analyses are

- Bacteriological Cure, i.e., Nugent’s score < 4
- Therapeutic Cure, defined as follows:
 - Clinical cure as defined in the Primary Endpoint
 - Vaginal pH < 4.7
 - Nugent’s score < 4 (i.e., Bacteriological Cure)

Total number and proportion of subjects achieving “Bacteriological Cure”, “Therapeutic Cure” (also each of the 3 components) will be presented for mITT population as well as PP population by study visit and treatment arm.

Nugent’s score will also be summarized categorically by its raw score (0, 1, 2, ..., 10). All results from the Amsel’s 4 criteria will also be summarized categorically (“Yes”/ “No”) by study visit and treatment arm for both mITT population and PP population.

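### mITT Clinical Cure is scored without regard to non-study BV-active drugs, so the study-sensitivity test can credit another drug's effect to the assigned gel; the direction of the error depends on which arm uses more

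*SAP*

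**What the plan says.** The study-sensitivity criterion in SAP 3.7.1 requires both active gels to beat placebo at p < 0.05 in mITT. Clinical Cure "includes the following 3 parameters from the" Study Procedure CRF page: discharge, whiff test and clue cells. They are taken from Visit 3, or from Early Termination for women who discontinued. If neither is available, "then the Visit 2 assessment results will be used". No other drug taken beforehand enters the scoring.

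SAP 3.4 contains three rules that might have done so:

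- **Antimicrobial use.** The first listed PP deviation is that the subject "Used topical or systemic antimicrobial drugs after randomization, this includes the following drug classes: antimycotics, antibacterials, antiprotozoals, gynecological anti-infectives" (the list continues). It acts on PP only.
- **Lack of efficacy.** "If lack of efficacy (LOE) is the discontinuation reason and the subject took at least 3 doses", she enters PP as a failure and the six deviations do not exclude her. This is written for PP only.
- **Imputed failure in mITT.** This covers early discontinuers who "do not have an assessment of Clinical Cure or Bacteriological Cure will be included in the mITT population as treatment failures". A woman who was assessed is outside it.

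SAP 3.4 also provides a review before database lock, but of "Other important violations that represent material non-compliance with study drug or protocol", that is, violations beyond the six listed, and it states no mITT outcome rule. Protocol 3.5.10 prohibits antibiotics and antifungals during the study without a scoring consequence. Protocol 9.2 and 9.6.1 add none.

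**The concern.** The placebo comparisons ask whether each gel clears BV better than vehicle. If a woman's BV persists, she takes an outside antibacterial or antiprotozoal and is then clear, the plan records a success for her assigned gel that the gel did not produce. This can happen in any arm, and its net effect on the comparison depends on how often it happens in each.

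The two populations can also disagree about the same woman. Suppose she stops for lack of efficacy after at least 3 doses and meets the three criteria at Early Termination. She is a failure in PP by rule and a cure in mITT by observation. Nothing in the SAP says this is intended.

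Study sensitivity is a pass/fail requirement for both active arms. What is at stake is its power and, under one pattern of use, its false-positive rate.

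**Working it through.** **Inputs from the documents.** 738 randomized 1:1:1, so 246 per arm (Protocol 3.1). 12.4% do not reach mITT (SAP 2.5): 246 × 0.876 = 215.5, taken as 215 per arm. Cure rates are 36% active and 20% placebo (SAP 2.5). The test is two-sided chi-square at 0.05 with active above placebo (SAP 3.1.2, 3.7.1). As a check that these inputs are read as intended, the continuity-corrected two-proportion formula at 90% power gives 176 per arm; 176 / 0.876 = 201, and 3 × 201 = 603, the plan's figure.

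**Assumed, because the documents are silent.** Let r be the share of would-be failures who take a BV-active drug, and c the share of those who then clear. The range for c starts at 36% (the plan's active cure rate), passes through 53% (98/185, once-daily label rate in Protocol Appendix 1) and ends at 70% (arbitrary). None of these is a clearance rate after treatment failure.

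**Formula.** Observed rate = p + (1 − p) × r × c. With equal r and c in all arms and f = r × c, the difference becomes 0.16 × (1 − f). For r = 10% and c = 70%, f = 0.07: active 0.36 + 0.64 × 0.07 = 0.4048, placebo 0.20 + 0.80 × 0.07 = 0.2560, difference 0.1488.

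**Equal use.** Power by exact enumeration; joint power conditions on the shared placebo count.

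| Use among failures | Clearance | Per comparison | Both comparisons |
|---|---|---|---|
| none | – | 96.2% | 93.1% |
| 5% | 36% | 95.1% | 91.3% |
| 5% | 53% | 94.5% | 90.3% |
| 5% | 70% | 93.9% | 89.4% |
| 10% | 36% | 93.8% | 89.2% |
| 10% | 53% | 92.4% | 87.1% |
| 10% | 70% | 90.9% | 84.6% |

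Per-comparison power reaches 90% at f = 0.0797. That is 215 × 0.80 × 0.0797 = 13.7 women cleared by another drug on placebo and 215 × 0.64 × 0.0797 = 11.0 in each active arm.

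**Heavier use on placebo** (10% of placebo failures, 5% of active failures). At 36% clearance the rates are 0.3715 and 0.2288, and power per comparison is 90%. At 80% clearance they are 0.3856 and 0.2640, and power is 77%.

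**Heavier use in an active arm, no true effect** (20% true cure in both arms; 10% of active failures, 5% of placebo failures). At 36% clearance the rates are 0.2288 and 0.2144, and the chance of a significant result favoring the active gel is 5.5%. At 80% clearance they are 0.2640 and 0.2320, and the chance is 11.7%. With equal use it is about 2.5%. These are per-comparison figures; the criterion needs both gels to succeed.

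**Equivalence.** SAP 3.7 states: "The PP population will be used to evaluate therapeutic equivalence between the test and reference product". In PP these women are excluded, or are failures if they stopped for lack of efficacy after at least 3 doses, so that test is largely shielded.

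**The case against.** The strongest reply is that nothing here is an error. Scoring outcomes as observed in mITT and handling deviations in PP is a recognized division of labor, and a SAP need not disclaim every rule it does not adopt. The pathway is narrow: the drugs are prohibited, and a drug taken after Visit 2 cannot affect a score carried forward from Visit 2. The discordant lack-of-efficacy case also needs a woman to be clear at Early Termination. Every rate above is assumed. A partial check already exists: the SAP 3.7.2 summaries, which include Clinical Cure as a component of Therapeutic Cure, "will be presented for mITT population as well as PP population by study visit and treatment arm". Finally, a rule tied to the recorded indication misses an antibacterial taken for another reason that also clears BV.

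Much of this stands. As-observed scoring is legitimate, the affected women may be few, and the sizes are illustrations. The limit of the recorded indication is real, which is why one sensitivity analysis below ignores indication. The PP summaries do not close the gap: they are descriptive, drop women with other deviations, and leave the pass/fail mITT test unchanged.

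A reader might infer that the scoring is simply conservative. That holds if use among placebo failures is at least about as common as among active failures; the documents do not establish this. A reader might equally infer that it manufactures superiority. That needs heavier use in an active arm, which the documents do not support either.

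**Conclusion.** The gap holds as an omission. SAP 3.7.1 counts an mITT woman cleared by a non-study BV-active drug as a cure of her gel, and SAP 3.4 lets a lack-of-efficacy discontinuer be a PP failure and an mITT cure. The direction of error is not fixed. Equal use, or heavier use on placebo, dilutes the 16-point difference; heavier use in an active arm could raise false superiority.

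Under equal use by 5-10% of failures and 36-70% clearance, the cost is modest: power per comparison goes from 96% to 91-95%, and for both from 93% to 85-91%. These sizes rest wholly on assumed usage and clearance. It would be wrong to infer that the equivalence conclusion is compromised, because that test uses PP. Low priority; confidence is medium.

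**What to change.** Change scoring only, before unblinding. State in SAP 3.7.1 that:

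1. the PP lack-of-efficacy failure rule also applies in mITT; and
2. an mITT subject is a non-cure if, after randomization and before the assessment used, she took a non-study systemic or vaginal antibacterial or antiprotozoal recorded as given for persistent or recurrent BV. Antifungal-only use does not trigger the rule.

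Extend the blinded pre-lock review in SAP 3.4 explicitly to identify these women. Concomitant medications and their indications are already recorded at Visits 2 and 3 and at Early Termination (Protocol 5.2 to 5.4). Report two sensitivity analyses: mITT as observed, and mITT with users of any BV-active drug scored as non-cures whatever the indication, from a drug list fixed before lock. Leave the PP definition as it is.

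The cost is a short scoring paragraph, a wider blinded review of existing data and two extra outputs. The downside is that the recorded indication may misclassify a few women; the two sensitivity analyses would show whether that matters.
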